Patient's susceptibility to DILI during treatment with anti-TB drugs is influenced by several drug- and host-related factors [102]. The most extensively studied potential causes of INH-induced DILI are related to those mechanisms. As to drug-related factors, acetylhydrazine, which is generated by NAT2, is widely considered as a crucial INH metabolite that contributes to INH-induced DILI. Given the importance of acetylation in INH metabolism, several studies have investigated into NAT2 loss of function polymorphisms as possible risk factors for DILI. In addition, advanced age [94], female gender [86], poor nutritional status [103], HBV or HCV infection [100] [104], HIV infection [78] [105], chronic liver disease, and alcoholism are environmental, physiological, and pathological factors contributing to DILI incidence. Moreover, the influencing variables differ according to racial and geographic characteristics.

Studies conducted in China demonstrated that approximately one-third of DILI patients had no symptoms, including some cases with severe liver injury [106] [107]. It has been demonstrated that screening patients for risk factors is useful in preventing disease progression, improving the outcome of therapy, and reducing mortality. However, rapid acetylators are very common in the Chinese population, so they are characterised by a lower susceptibility to develop DILI. Our patient cohort is multi-ethnic, with a prevalence of Caucasians and so a higher frequency of slow acetylator status. For this reason, our objective is to corroborate the conclusions drawn by the previous studies through the examination of our complementary data.

Outcome measures and assessments

The primary outcome is to determine the association between risk factors (drug- and host-related factors) and the incidence of DILI.

The primary outcome measures are the occurrence of anti-TB DILI (number of participants with DILI), which was defined by: 1) AST or ALT level > 5 times the ULN in patients with absence of symptoms or with total BIL level > 2 times the ULN, or 2) AST or ALT level > 3 times the ULN and total BIL level > 3 times the ULN in patients who show symptoms compatible with hepatitis.

The secondary outcome is to evaluate the characteristics of patients who first experienced anti-TB DILI. The secondary outcome measures are the prevalence of early hepatotoxicity experience.

Methods

Study design

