This is a retrospective observational study, no profit, to determine environmental, physiological, and pathological factors associated with the incidence of DILI during anti-TB treatment. Data collected from patients with confirmed tuberculosis, enrolled at the Department of Infectious Diseases of Luigi Sacco Hospital in Milan, Italy, between July 2020 and September 2023, will be analysed. Subjects were all followed up as outpatients at Tuberculosis Clinic at Luigi Sacco Hospital, some of them with previous inward stays at various hospitals in the Lombardy Region.

Study population

The following are the inclusion criteria: 1) adult patients (>18 years), 2) patient who received standard initial therapy including INH (5mg/kg), RMP (10mg/kg), and PZA (25mg/kg) for patients with active TB disease, 3) treatment with first line anti-TB drugs, including rifampicin and isoniazid for patients with latent TBI, 4) normal serum ALT and bilirubin levels, no symptoms related to abnormal liver function prior to anti-TB drug treatment and 5) informed consent. Patients with any of the following conditions are excluded from the study: 1) liver dysfunction, including biliary origin, before anti-TB therapy, 2) patients receiving non-standard treatment regimen initially (e.g., patients with severe pulmonary or extrapulmonary TB receiving large doses or more than four anti-TB drugs), 3) modified treatment regimen due to drug resistance or intolerance excluding first line anti-TB drugs, 4) lactation or pregnancy, 5) concomitant use of hepatotoxic drugs, 6) abnormal hepatic function on laboratory testing before anti-TB, 7) disease that was resistant to INH at the start of treatment or 8) patients refusing to sign informed consent.

The participants were given standard anti-TB treatment in line with international guidelines (RMP 10 mg/kg, INH 5 mg/kg), primarily administered orally, although intravenous administration was

employed for inpatients as needed, and modified to oral administration as soon as possible. The other drugs of the standard regimen included standard daily doses of PZA (15-30 mg/kg) and EMB (15-20 mg/kg).

Data collection

Data that will be collected include clinical, biochemical, and genotyping findings that are typically used in clinical practice to manage and monitor tuberculotic patients at Luigi Sacco Hospital. The complete list of parameters (host- and drug-related factors) is provided below:

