- Clinical data: age, weight, height, gender, ethnicity, hepatotoxicity or alcoholism, duration of anti-TB treatment, tuberculosis site (pulmonary or extra), adverse event, concomitant infection (HIV, HAV, HCV, HBV), past medical history, concomitant drugs. Patient's nutritional status was reported as BMI, which was calculated based on height and body weight;
- Biochemical data: ALT, AST, GGT and BIL;
- Laboratory data: NAT2 acetylator status. The acetylation status of patients will be assigned like as suggested by earlier research:
 - rapid acetylator: NAT2*4 is a wild-type allele (defined by absence of slow alleles);
 - intermediate acetylator status: carry one copy of NAT2*4 and one defective variant allele (NAT2*5, *6, *7, and *14);
 - slow acetylator: two copies of slow variant allele (NAT2*5, *6, *7, and *14).

Statistical analysis

Sample size calculation

[figure not shown]
We are planning a study of matched sets of cases and controls with 2 matched controls per case. Prior data indicate that the probability of exposure among controls is 50%, and the correlation coefficient for exposure between matched cases and controls is -0.2 [10] [108] [109] [110] [111]. If the true odds ratio for disease in exposed subjects relative to unexposed subjects is 3, we will need to study 40 case patients with 80 matched controls to be able to reject the null hypothesis that this

odds ratio equals 1 with a power of 80%, assuming that the Type I error probability associated with the test of this null hypothesis is 5%.

[figure not shown]
Parameters: Exposure in cases = 75%; Exposure in controls = 50%

Absolute difference = 25%; Relative difference = 50%; Odds ratio = 3

Sample sizes across range of OR and control exposure, with inputted values:

Number of cases required varying ratio of controls per case, other inputs constant:

We will use a nested case-control study design that takes into account time of events occurrence in sampling of controls. For each case, one or more controls are selected from the risk set at the time in which the event of interest occurred in the case. The risk set means the set of all individuals that are still “events-free” and not censored. Therefore, they are still included in the study at that time, thus, eligible to experience the event now observed in the case. As a consequence, individuals can

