be sampled as controls for more than one case and, in turn, individuals sampled as controls may subsequently become cases. Cases and controls will be matched according to baseline variables, including age, sex, and BMI, and then conditional regression analysis (a type of matched statistical analysis) will be performed to draw associations.

Data management

All data are retrieved from the patient's medical record. Variables will be entered into the eCRF by site staff, who will be trained on how to use the eCRFs and capture the data required by the protocol. The eCRF is an electronic data entry media and should not constitute the original (or source) medical record. Data derived from source documents and reported in the eCRFs should be consistent with the source documents, or the discrepancies should be explained in these source documents. The investigator must complete the eCRF for each participant. The investigator's signature on the eCRF will attest to their accuracy and completeness.

Data collected from each participant will be anonymized: each subject will be assigned a unique code so that only the investigator will be able to identify the subject. The file associating the participant's code with their identifying data will be stored separately on a password protected computer. The study database will be password protected and uploaded to a computer that is also password protected and accessible only to study personnel designated by PI. Identification of the data will be done in such a way that individuals accessing the database will not be able to trace the identity of the subjects in any way.

The study will involve statistical calculations on collected data using literature standard methods to identify and correlate variables (Chi-square, Fisher's exact, Mann-Whitney U-test, conditional regression). The results will be published in medical journals and presented at conferences. Study data will be retained for 7 years starting from the study's conclusion. Data processing will be done in strict compliance with GDPR and any applicable national legislation.

Potential Benefit of the Study

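### Age, sex and BMI are matching variables, yet they are also host factors under the primary outcome, and no analysis outside the matched sets is specified for them

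*Protocol*

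**What the plan says.** Under Outcome measures and assessments: "The primary outcome is to determine the association between risk factors (drug- and host-related factors) and the incidence of DILI". The background section on host factors discusses age, gender and nutrition. Rationale and Aims lists older age, female sex and poor nutrition among the "environmental, physiological, and pathological factors contributing to DILI incidence". Study design states the aim in nearly the same terms: "to determine environmental, physiological, and pathological factors associated with the incidence of DILI during anti-TB treatment". Data collection fixes the nutritional measure: "nutritional status was reported as BMI, which was calculated based on height and body weight".

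Under Sample size calculation, "we will need to study 40 case patients with 80 matched controls", with two controls per case. Controls come from risk sets: "one or more controls are selected from the risk set at the time in which the event of interest occurred in the case". The last sentence of that section reads "Cases and controls will be matched according to baseline variables, including age, sex, and BMI", and conditional regression follows as the means of drawing associations. No caliper, category or exact-match rule is given.

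Data management also lists chi-square, Fisher's exact and Mann-Whitney tests. It does not say which variables they apply to, or whether they use the matched sample or all eligible patients.

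**The concern.** A matched analysis compares a case only with its own controls. A variable used to form the set is held equal, or nearly equal, within it, so the comparison says little or nothing about that variable's own effect. Here three variables are both part of the question and part of the matching.

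At stake is a misleading negative result. The background cites a 3.5-fold risk over age 60 and a 4-fold risk in women. A matched sample would show nearly balanced age, sex and BMI by construction, and a reader could take that balance as evidence that these factors do not matter. Choosing the caliper later does not bring back a sex effect lost to exact matching. That needs a different analysis set.

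**Working it through.** **1. The plan's own figure.** Inputs from Sample size calculation: 2 controls per case, exposure 50% in controls and 75% in cases, OR ψ = 3, correlation −0.2, 5% type I error (taken as two-sided), 80% power. In Dupont's formula for matched sets, t_k is the probability that k of the 3 set members are exposed, π_k(ψ) = kψ/(kψ + 3 − k), e = Σ t_k π_k and v = Σ t_k π_k(1 − π_k), with k = 1, 2.

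- t₁ = 0.343, t₂ = 0.483
- At OR 1: e = 0.4366, v = 0.1837. At OR 3: e = 0.6202, v = 0.1416
- n = (0.8416·√0.1416 + 1.960·√0.1837)² / (0.6202 − 0.4366)² = 1.338/0.0337 = 39.7

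Solving the case exposure from the matched OR instead gives 40.2. The stated 40 cases reproduce. With correlation 0 the result is 43.7, that is 44 cases.

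**2. Sex, if matched exactly.** Only sets with k = 1 or 2 count in that formula. With exact matching k is always 0 or 3, so no set counts. In the conditional likelihood each set contributes ψˣ/(3ψˣ) = 1/3 whatever ψ is. The information is zero.

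**3. Age and BMI, matched within ±c SD (assumed; the protocol gives no c).** Take controls spread uniformly around the case, with variance c²/3.

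- Expected within-set variance: (2/3)(c²/3) − (2/9)(c²/3) = 4c²/27
- Without matching: 2/3
- Ratio: (4c²/27)/(2/3) = 0.222c²

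| Caliper | Information left | Power, OR 2 per SD | Power, OR 1.5 per SD |
|---|---|---|---|
| none | 100% | 94% | 56% |
| 1 SD | 22% | 55% | 18% |
| 0.5 SD | 5.6% | 17% | 4% |
| 0.25 SD | 1.4% | 3% | 2% |

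Powers are simulated score tests with 40 sets. Matching in bands behaves alike: at an assumed age SD of 15, 10-year bands leave (10²/12)/15² = 8.3/225 = 3.7% of the variance, and 20-year bands leave 33.3/225 = 14.8%.

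**4. Illustration with risk-set sampling.** Assumptions: cohort 143 to 800 (40/0.28 and 40/0.05, from the 5% to 28% incidence in the background); age uniform 20 to 80, or mean 42 and SD 15; 40% women; BMI mean 22, SD 3.5; sex matched exactly; 1:2 sampling. The table gives the number of the 40 sets that carry information.

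| Factor | Matched on time only | ±10 y, ±4 kg/m² | ±5 y, ±2 kg/m² |
|---|---|---|---|
| Sex | 30–31 | 0 | 0 |
| Age over 60 | 15–31 | 6–8 | 2–4 |
| BMI below 18.5 | 17–19 | 9–11 | 4–6 |

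A crude OR for age over 60 computed inside the tighter matched sample comes out at about 1.1 to 1.6 when the true ratio is 3.5. This is the pull towards no difference that the unmatched tests would show there.

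**5. What the full cohort could give, with 40 events.** Cox model with age over 60, sex and BMI below 18.5 together, same assumptions, no other censoring:

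- Age over 60: power 86% to 98% for 3.5-fold, 67% to 87% for 2.6-fold
- Sex: 98% to 99% for 4-fold, 58% to 63% for an assumed 2-fold
- BMI below 18.5: 43% to 50% for an assumed 2-fold

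A simpler check for sex, comparing 40 cases with all non-cases at 30% to 50% women, gives 93% to 99% at OR 4, 79% to 93% at OR 3 and 43% to 58% at OR 2.

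**The case against.** Four arguments weigh on the other side.

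*The analysis set can be left to a SAP.* The study plans to analyse data from patients enrolled over a stated period, its outcome measure is a count of participants with DILI, and the listed unmatched tests could be run on everyone. This stands in part: nothing forbids a full-cohort analysis, and because the study is retrospective, matching destroys no data. But the protocol itself fixes the matching variables and names conditional regression as the way to draw associations. It exempts none of the three factors from that route.

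*The loss for age and BMI depends on the caliper.* This stands. A 1 SD caliper leaves a reduced but usable amount, and at ±4 kg/m² more than half of the informative BMI sets remain. A reader might infer that age and BMI cannot be assessed at all; the protocol does not support that, because it gives no matching rule. For the same reason the statement about sex is conditional on exact matching.

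*Matching on known risk factors is legitimate when NAT2 is the main interest.* This also stands for NAT2. It does not settle the point, because the outcome and aim sections present the three as factors to be assessed and not merely as confounders.

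*The benchmark effects are imperfect.* The 2.6-fold figure concerns pyrazinamide-related adverse events in general. The title of the source for the 4-fold sex effect concerns rifampin and pyrazinamide in latent infection. Both therefore serve only to show scale.

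**Conclusion.** The concern holds, within limits. The protocol places age, sex and nutritional status under its primary outcome and then matches on all three in the only association analysis tied to its sampling design. The sex main effect is not estimable if sex is matched exactly. Age and BMI keep roughly 0.22 times the squared caliper (in SD) of their information: modest at 1 SD, very little at 0.5 SD or tighter. Unmatched tests of the three in the matched sample would be biased towards no difference.

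A reader might go further and conclude that the primary outcome as a whole fails, or that the sample size is wrong. The documents do not support either. Factors not used for matching are untouched by this problem, and the 40-case figure reproduces from its stated inputs. One caution applies: the word including in the matching sentence leaves the list open, so which factors are unmatched is not yet settled.

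The power figures rest on an assumed cohort size and on assumed age, sex and BMI distributions. I would rank this as something that should be fixed, not as a defect that stops the study.

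**What to change.** In the statistical section, close the list of matching variables, keep the matched conditional analysis for NAT2 and the other unmatched factors, and add wording such as:

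> Age, sex and BMI are the matching variables. Their main effects will not be drawn from the matched sets. They will be estimated in all eligible patients by Cox regression on time to DILI with the three factors together, adjusted for or stratified by active TB versus latent infection. Any chi-square, Fisher's exact or Mann-Whitney test of these three factors will use all eligible patients.

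The disease-state term is needed because the study admits both groups, on different regimens.

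Alternatively, state that the three are treated only as confounders and remove them from the factors under the primary outcome.

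Cost: no added patients and no change to the 40 cases and 80 controls. Age, sex, BMI, disease state and follow-up time must be extracted for the whole cohort; risk-set matching already needs most of this for every potential control. The extra model has few events per term (40 events over four terms is 10 each), and its power for 2-fold effects is about 60% or less under the assumptions above. The three factors and NAT2 would be estimated in different analyses, and adjusting the three for NAT2 would need genotypes for the whole cohort.

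Matching on time only, with the three as covariates, is not recommended as a shortcut. The 40 cases rest on a correlation of −0.2 within matched sets, which need not carry over; at correlation 0 about 44 would be needed.
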